8.6 Patient Consent

Patients who meet all of the inclusion criteria and none of the exclusion criteria will be invited to participate in this study. All patients eligible for entry will have the clinical study explained to them, as well as potential risks and benefits of their participation in the study. Each patient who agrees to participate will be required to sign and date an informed consent document prior to the procedure or any study-specific testing. If approved by the local Ethics Committee/IRB, a legally authorized representative may provide consent on behalf of the patient.

If new information is obtained after a patient receives treatment with the device, patients who have not exited the study will be informed about the new information, and will be reconsented at the discretion of the investigator and/or the site's Ethics Committee/IRB.

8.7 Point of Enrollment

Point of enrollment will be based on the intent-to-treat population, and is defined to include any patient for which the treatment procedure is initiated. More specifically, once a procedure has begun (i.e., cutdown or percutaneous access initiated), this patient would be included in the intent-to-treat population. The patient's informed consent will be obtained and assessment of the patient's conformance to the inclusion/exclusion criteria will occur prior to the procedure.

8.8 Methods

8.8.1. Medication

The hospital's standard protocol should be followed with respect to medication.

8.8.2. Pre-procedure

Grafts are sized based on the findings from preoperative radiologic studies, including computerized tomography (CT) or conventional angiography. Refer to the Instructions for Use for details regarding the suggested imaging studies to be obtained and sizing guidelines.

8.8.3. Procedure

Standard techniques for placement of arterial access sheaths, guiding catheters, angiographic catheters and wire guides should be employed during use of the Zenith Low Profile AAA Endovascular Graft and the Zenith Spiral-Z AAA Iliac Leg Graft. The Zenith Low Profile AAA Endovascular Graft and the Zenith Spiral-Z AAA Iliac Leg Graft are compatible with 0.035 inch diameter wire guides.

Refer to institutional protocols relating to anesthesia, anticoagulation and monitoring of vital signs. Refer to the Instructions for Use for complete details regarding use of the Zenith Low Profile AAA Endovascular Graft and the Zenith Spiral-Z AAA Iliac Leg Graft. Fluoroscopic guidance and angiography should be used throughout the procedure to verify positioning of the devices with respect to the patient's anatomy.

The iliac leg graft should overlap with the main body limb by at least one stent, as inadequate overlap (< 1 stent) may increase the risk for migration and/or endoleak. Excessive overlap of the iliac leg graft with the main body (leg component more than 10 mm above the main body bifurcation) may restrict flow and thereby increase the risk of limb thrombosis. Additionally, the proximal edge of the ipsilateral leg graft should align closely with that of the contralateral leg graft (i.e., the ends of both graft legs should be at the same height relative to the graft bifurcation).

If the distal seal of the iliac leg graft lands in a location different from that used to select the graft size, undersizing or excessive oversizing could result. Excessive oversizing may result in flow restriction with higher risk of limb thrombosis and

should be treated appropriately at the time of procedure (e.g., with adjunctive balloon dilatation and/or stent placement).

Pre-existing regions of stenosis/narrowing less than approximately 20 mm ID in the aorta or 7-8 mm ID in the iliac arteries may increase the risk for limb thrombosis if left untreated. Dilatation of these regions with a noncompliant balloon and/or stent placement may be necessary to help assure continued graft patency. The completion angiogram (with stiff wire guides removed) should be reviewed carefully to determine whether further treatment in these regions is necessary (e.g., adjunctive balloon dilatation/stent placement). Failure to remove the stiff wire guide prior to the angiogram could mask any limb kinking or narrowing that might occur when the wire guide is removed.

Both graft leg lumens should be evaluated carefully in multiple views at the completion of the procedure to assess for any narrowing and to document the minimum graft lumen ID. Patients with a graft leg lumen less than approximately 5 mm ID may be at increased risk for limb thrombosis. Intervention (e.g., noncompliant balloon dilatation and/or stent placement) should be considered to help assure continued graft patency.

8.8.4. Peri-operative Care

The endovascular method does not require any departure from the usual peri-operative management of patients undergoing aneurysm repair.

8.8.5. Post-operative Treatment of Endoleaks

Type I and type III endoleaks warrant immediate treatment. Type II endoleaks should be treated at the physician's discretion, depending on aneurysm behavior and size, endoleak source, and time from implantation. If the aneurysm is enlarging, treatment by embolization or ligation should be considered. Type III endoleaks should be treated with additional ballooning or prostheses.

8.9 Criteria and Procedures for Study Termination

A patient's follow-up in the study will end after:

- 1) Failure to deploy the device + 30 days;
- 2) Conversion to open surgical technique + 30 days;
- 3) Patient withdrawal or lost to follow-up;

- 4) Patient death;
- 5) Closure of the investigation; or
- 6) Completion of all scheduled clinical and imaging visits through 5 years.

No medical care related to the clinical study will be provided for the subjects after study completion.

8.10 Sample Size

This investigation will enroll a maximum of 120 subjects at a maximum of 40 investigative sites. Patient recruitment is expected to be completed within 12 months of initiating the study. Follow-up data will continue to be collected for 5 years after graft deployment for each patient in the study, making the study duration at least 72 months.

8.11 Period of Use for the Device or its Control

The 5-year follow-up period of the clinical investigation should permit the demonstration of performance over a period of time sufficient to represent a realistic test of the performance of the device and allow identification and risk assessment of any associated adverse device effects over that period.

8.12 Limitations of the Investigation

This study is inherently limited by the number of patients who will be excluded due to general, medical, and anatomical exclusion criteria. Additional challenges of the study include the anticipated comorbidities likely to be found in patients with aortic, aortoiliac, or iliac aneurysms, which may confound data analysis. Additional confounding elements of the study might include the lower incidence of AAA in women, with the anticipation of fewer women than men being enrolled in the study.

8.13 Safety Monitoring

Safety monitoring will include collecting data regarding adverse events. Section 7, Risk Analysis, lists the potential adverse events associated with this study.

A Data Safety Monitoring Board (DSMB) consisting of independent physicians and at least one independent statistician, who are not investigators in the study, nor have a perceived conflict of interest with the conduct and administration of

the study, will be convened on a regular basis to evaluate the study progress and review adverse events.

An independent Clinical Events Committee (CEC) will be established to adjudicate clinical events reported during the study. This adjudication will be performed according to standard operating procedures to assess whether the events were due to a pre-existing condition, procedure-related, technique-related, and/or device-related. In addition, a core lab will be established to independently review available imaging.

Regular scheduled monitoring, including on-site visits, will be conducted, in part, for identification of adverse events and assurance that they are correctly reported to the DSMB, CEC, and Ethics Committees/IRBs.

In addition, incidences of intra-operative conversion to open surgical aneurysm repair, access failure, and intra-operative type I or type III endoleak will be evaluated by the sponsor on a case-by-case basis. If a potential safety issue is identified, the sponsor may delay additional enrollment until further investigation into the incident is performed.

9.0 Statistical Considerations

9.1 Sample Size Calculations

Evaluation of the safety hypothesis, 30-day freedom from MAEs, requires 46 patients to determine whether the performance goal of 88% has been met. Evaluation of the effectiveness hypothesis, 12-month device success, requires 59 patients to determine whether the performance goal of 83% has been met. Cook intends to enroll 120 patients to account for patients who withdraw or are lost to follow-up, and also to provide added enhanced statistical certainty as well as the same number of patients as agreed to for a previous similar study.

Sample size calculations for the safety and effectiveness hypotheses can be performed with the following assumptions. Using performance goals of 88% for freedom from MAEs and 83% for device success, with an expected rate of 99.2% for freedom from MAEs and 93.5% for device success, an exact binomial calculation, $\alpha=0.025$, power=0.80 and a one-sided test, 46 patients for freedom

from MAEs and 59 patients for device success are required to demonstrate that the Zenith Low Profile AAA Endovascular Graft in conjunction with the Zenith Spiral-Z AAA Iliac Leg Graft meets the stated performance goals.

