4.3 Specific Hypotheses to be Accepted or Rejected by Statistical Data

The safety endpoint of 30-day freedom from MAEs will be analyzed on a per patient basis. The analysis requires that the agreed upon performance goal of 88%, which was derived from the 30-day freedom from MAE rate for patients treated with the currently approved Zenith AAA Endovascular Graft, be met. The performance goal will be said to have been met provided that the null hypothesis is rejected in favor of the alternate with a one-tailed exact binomial test at the 0.025-level. Given that $\pi_{MAE(30)}$ is the probability that a randomly selected patient experienced freedom from MAEs at 30 days, the null and alternate hypotheses are as follows.

Null Hypothesis: The 30-day freedom from MAEs for patients treated with the Zenith Low Profile AAA Endovascular Graft in conjunction with the Zenith Spiral-Z AAA Iliac Leg Graft does not meet the performance goal (88%).

$$H_0: \pi_{MAE(30)} < 88\%$$

Alternate Hypothesis: The 30-day freedom from MAEs for patients treated with the Zenith Low Profile AAA Endovascular Graft in conjunction with the Zenith Spiral-Z AAA Iliac Leg Graft meets the performance goal (88%).

$$H_A: \pi_{MAE(30)} \geq 88\%$$

Similarly, the effectiveness endpoint of 12-month device success will be analyzed on a per patient basis. The analysis requires that the agreed upon performance goal of 83%, which was derived from the 12-month device success rate for patients treated with the currently approved Zenith AAA Endovascular Graft, be met. The performance goal will be said to have been met provided that the null hypothesis is rejected in favor of the alternate with a one-tailed exact binomial test at the 0.025-level. Given that $\pi_{DS(12)}$ is the probability that a randomly selected patient experienced device success at 12 months, the null and alternate hypotheses are as follows.

Null Hypothesis: The 12-month device success for patients treated with the Zenith Low Profile AAA Endovascular Graft in conjunction with the Zenith Spiral-Z AAA Iliac Leg Graft does not meet the performance goal (83%).

$$H_0: \pi_{DS(12)} < 83\%$$

Alternate Hypothesis: The 12-month device success for patients treated with the Zenith Low Profile AAA Endovascular Graft in conjunction with the Zenith Spiral-Z AAA Iliac Leg Graft meets the performance goal (83%).

$$H_A: \pi_{DS(12)} \geq 83\%$$

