9.2 Performance Goals

The performance goals used for the hypotheses in section 4.3 and the sample size calculations in section 9.1 were derived from the pivotal study of the Zenith AAA Endovascular Graft. The 30-day freedom from MAEs was 98.3% and the 12-month device success was 93.0% in the pivotal study of the Zenith AAA Endovascular Graft. Therefore, the performance goals of 88% for freedom from MAEs and 83% for device success, respectively, have been determined.

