9.4 Missing Data

Missing data will be addressed using three primary strategies: 1) estimating missing data with the best available data, 2) case deletion, and 3) multiple imputation.

The first strategy may be used for missing imaging data. Previous clinical trial experience suggests that some portion of the imaging data may not meet the criteria for accurate measurements by the core laboratory. However, it is recognized that the treating physician uses this information to provide the best possible care for the patient. Therefore, it is reasonable to substitute any missing core laboratory measurements with the corresponding measurements made by the treating physician (or his/her staff). In addition, the absence or presence of clinical sequelae may provide the required missing core laboratory assessment of device performance. This strategy is a best approximation of the missing data value.

The second strategy is case deletion. If the amount of missing data does not result in a reduction of analyzable patients to a number that is below that required for sufficient statistical power of the endpoints, then case deletion will be the method of choice for that analysis.

The third method is multiple imputation. This method will be used to predict missing endpoint or covariate data. It may be that the study endpoints may depend upon certain covariates. Therefore, it may be possible to model study endpoints, given a series of related covariates. This model-based imputation exercise may provide estimates of the missing data that can be utilized in estimating event rates and confidence bounds.

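### The 59 patients stated for 12-month device success give 66% exact power at one-sided 0.025, not 80%; the stable requirement is 89

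*Combined protocol and SAP*

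**What the plan says.** Section 4.3 tests 12-month device success against a performance goal of 83% with a "one-tailed exact binomial test at the 0.025-level". Section 9.1 sizes both primary endpoints under one set of assumptions. The goals are those of section 4.3 (safety 88%, effectiveness 83%), the anticipated true rates are 99.2% and 93.5% respectively, and the method is exact binomial at alpha 0.025 with "power=0.80 and a one-sided test". On effectiveness it concludes: "Evaluation of the effectiveness hypothesis, 12-month device success, requires 59 patients to determine whether the performance goal of 83% has been met". For safety the figure is 46. Enrolment is set at 120, to cover withdrawal and loss to follow-up, to add statistical certainty, and to match an earlier similar study. No attrition rate is given.

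Section 9.2 reports the rates behind the goals: "The 30-day freedom from MAEs was 98.3% and the 12-month device success was 93.0% in the pivotal study".

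Section 9.4 makes case deletion the preferred method for missing data unless it would cause "a reduction of analyzable patients to a number that is below that required for sufficient statistical power of the endpoints". It prints no number of its own.

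**The concern.** Section 9.1 supplies every input to the effectiveness calculation, so 59 should be reproducible. It is not. An exact one-sided test at 0.025 with 59 patients falls well short of 80% power.

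Two things depend on the figure. First, it is the stated sample size and power for a primary endpoint, and it sets how much of the 120 looks like spare capacity. Second, section 9.4 turns on the number required for sufficient power. If that number is 59, complete-case analysis of device success stays the preferred method even when about half the cohort has no 12-month result. The trial could then be presented as fully powered when it is not.

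**Working it through.** **Inputs.** p0 = 0.83, p1 = 0.935, one-sided alpha 0.025 and target power 0.80 (sections 4.3 and 9.1). The alternative p1 = 0.930 is the pivotal-study rate in section 9.2. Planned enrolment is 120.

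**Method.** For X ~ Binomial(n, p), let r be the smallest integer with P(X ≥ r | p0) ≤ alpha. Power is P(X ≥ r | p1). The required n is the smallest with power ≥ 0.80. Exact power is saw-toothed in n, so I also give the n from which it stays at or above 0.80.

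**Step 1: the plan's figure, n = 59, p0 = 0.83.**
- P(X ≥ 54 | 0.83) = 0.0499, which exceeds 0.025, so 54 successes are not enough.
- P(X ≥ 55 | 0.83) = 0.0196, so r = 55.
- Power = P(X ≥ 55 | 0.935) = 66.2%. At p1 = 0.930 it is 60.3%.

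The stated 80% is not reproduced.

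**Step 2: the n that the stated inputs require (p1 = 0.935, alpha 0.025).**

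| n | r | actual alpha | power |
|---|---|---|---|
| 59 | 55 | 0.0196 | 66.2% |
| 74 | 68 | 0.0228 | 79.5% |
| 80 | 74 | 0.0116 | 73.7% |
| 81 | 74 | 0.0250 | 84.4% |
| 86 | 79 | 0.0146 | 80.4% |
| 87 | 80 | 0.0131 | 79.6% |
| 88 | 81 | 0.0118 | 78.7% |
| 89 | 81 | 0.0243 | 87.6% |
| 120 | 108 | 0.0222 | 95.1% |

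Between 59 and 80, power runs from 58.4% to 79.5% and never reaches 80%. The first n to do so is 81. Power dips below 80% again at 87 and 88 and stays above it from 89. At p1 = 0.930 the first n is 89 and the stable n is 97, and power at 120 is 92.3%.

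**Step 3: where 59 could come from.** At one-sided alpha 0.05 and n = 59, r = 54, actual alpha is 0.0499 and power is 81.6%. At n = 58 power is only 67.5%, and 59 is the smallest n reaching 80% at that alpha. Other methods at alpha 0.025 do not give 59:
- mid-p: same cut-off and the same 66.2% at n = 59
- normal approximation: 81, or 91 with continuity correction
- null variance only: 101
- alternative variance only: 44
- arcsine: 71

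**Step 4: the safety figure as a control (p0 = 0.88, p1 = 0.992).** At alpha 0.025 the smallest n is 45 (r = 44, power 94.9%). The stated 46 has r = 45, actual alpha 0.0203 and power 94.7%, so it agrees within one patient. At alpha 0.05 the smallest n would be 24. The two stated figures therefore do not fit a single alpha.

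**Step 5: losses from 120 before the requirement is breached.**
- Requirement 59: 120 − 59 = 61 (51%)
- Requirement 81: 120 − 81 = 39 (33%)
- Requirement 89: 120 − 89 = 31 (26%)
- Requirement 97 (if p1 = 0.930): 120 − 97 = 23 (19%)

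**The case against.** The best reply is that the trial is not underpowered. It plans 120 patients, giving 95.1% power if all are evaluable, and still 87.0% with 90 evaluable, a loss of 25%. The decision rule stays at 0.025 whatever section 9.1 prints, so type I error is untouched. The risk is of failing a device that works, not of passing one that does not. All of this stands, and it is why no extra enrolment is needed.

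Three further points are fair as limits on the claim:
- No attrition allowance is stated. The 61 is obtained by subtraction.
- Section 9.4 neither prints 59 nor cites section 9.1. Reading 59 into it is an inference, and a statistician could recompute the requirement. The harm would also need about half of the 12-month results to be missing, after section 9.4's first strategy of substituting site measurements has been used.
- That alpha 0.05 was used is inferred from an exact match. The safety figure misses the first-n rule by one patient, so the sponsor's search rule is not known.

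None of these rescues the 59. It is wrong for the inputs printed beside it, and section 9.1 offers no other required number for section 9.4 to rely on.

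**Conclusion.** The concern holds. On the plan's own inputs, 59 patients give 66.2% power, so a device performing exactly as assumed would fail the test about one time in three (1 − 0.662 = 0.338). At a true rate of 93.0%, power is 60.3%. The requirement for 80% power is 81 at first reach and 89 as a stable floor.

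The figures for n = 59 and the corrected requirement rest only on the test, alpha and rates in sections 4.3, 9.1 and 9.2. The origin in a doubled alpha and the link to section 9.4 are inferences, both well supported. The planned enrolment of 120 is sound. What must be corrected is the stated requirement for a primary endpoint and any missing-data decision based on it.

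**What to change.** In section 9.1:
- Replace 59, in both places where it appears, with 89, described as the smallest number from which exact power stays at or above 80% at one-sided 0.025. If 81 is mentioned, label it as the first number to reach 80%. It is a poor floor, because power falls below 80% at 87 and 88.
- State the power with 120 evaluable patients: 95.1% at 93.5% and 92.3% at 93.0%.
- State the loss that can be absorbed: about 31 of 120 at 93.5%, or 23 of 120 if the pivotal rate of 93.0% is used for planning.

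In section 9.4, name the number that triggers a move away from case deletion for device success and make it the corrected one.

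Leave alpha at 0.025. Keeping 59 with a cut-off of 54 successes would raise the type I error to 0.0499, about twice the stated level.

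The cost is wording in two sections. No patients, visits or procedures are added, but the margin for missing 12-month data becomes visibly smaller.

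### The 59 patients stated for 12-month device success give 66% power, not 80%, at the plan's own inputs, and the case-deletion rule in Section 9.4 appears to depend on that number

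*Combined protocol and SAP*

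**What the plan says.** Section 4.3 tests each endpoint against its performance goal "with a one-tailed exact binomial test at the 0.025-level". Section 9.1 sizes the study on the same terms: an exact binomial calculation, alpha 0.025, "power=0.80 and a one-sided test". The null rates are the goals ("Using performance goals of 88% for freedom from MAEs and 83% for device success") and the alternatives are given as "with an expected rate of 99.2% for freedom from MAEs and 93.5% for device success". No source is cited for the two alternatives. The results are that safety "requires 46 patients to determine whether the performance goal of 88% has been met" and effectiveness "requires 59 patients to determine whether the performance goal of 83% has been met". Planned enrolment is 120, to allow for withdrawal and loss to follow-up and to add statistical certainty; no dropout rate is given.

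Section 9.2 explains the goals: "The 30-day freedom from MAEs was 98.3% and the 12-month device success was 93.0% in the pivotal study" of the predecessor graft. These are the only observed rates in the document.

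Section 9.4 makes case deletion the preferred handling of missing data unless it would reduce the analysable patients to "a number that is below that required for sufficient statistical power of the endpoints". It does not say what that number is.

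**The concern.** All the inputs needed to check 59 are stated, so it should reproduce, and it does not. A wrong required size would matter little if it were only background to an enrolment of 120. Here it may also act as a rule. Section 9.4 makes the choice between deleting incomplete cases and imputing them depend on a required number, and 46 and 59 are the only required numbers in the document. If 59 is too small, the effectiveness analysis could lose many patients at 12 months and still be described as adequately powered. Device success is the endpoint with the longer follow-up and with imaging components, so it is the one more exposed to missing data.

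A second, smaller question is why the assumed rates (99.2% and 93.5%) exceed the pivotal rates (98.3% and 93.0%) without explanation.

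**Working it through.** **Inputs.** Null rates 0.88 and 0.83, alternatives 0.992 and 0.935, alpha 0.025 one-sided, power 0.80, stated sizes 46 and 59 (Sections 4.3 and 9.1). Pivotal rates 0.983 and 0.930 (Section 9.2).

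**Formula.** For X ~ Binomial(n, p), the critical value r is the smallest integer with P(X ≥ r | n, p0) ≤ alpha. Power is P(X ≥ r | n, p1). Because r is an integer, power rises and falls in a saw-tooth as n grows. I therefore give both the first n that reaches 80% and the n from which power stays at or above 80%.

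**Step 1: safety, the plan's figure.** With p0 = 0.88 and p1 = 0.992, the first n reaching 80% is 45 (power is 70.2% at 44 and 95.0% at 45). At the stated 46, r = 45, attained alpha is 0.0203 and power is 94.7%. The stated size reproduces to within one patient. At the pivotal 98.3%, power at 46 is 81.6%, still above target.

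**Step 2: effectiveness, the plan's figure.** With p0 = 0.83, p1 = 0.935 and n = 59:

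- P(X ≥ 54 | 0.83) = 0.0499, which exceeds 0.025, so 54 successes are not enough.
- P(X ≥ 55 | 0.83) = 0.0196, so r = 55.
- Power = P(X ≥ 55 | 0.935) = 66.2%.

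The stated 59 does not give 80%. Approximate methods at alpha 0.025 do not recover it either: the normal approximation gives 81, the arcsine method 71, and the version using only the alternative's variance 44.

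**Step 3: what 59 does match.** At one-sided alpha 0.05, 54 of 59 is sufficient (0.0499), power at 93.5% is 81.6%, and 59 is the first n to reach 80%. The safety size cannot come from alpha 0.05: its first n there would be 24. The two stated sizes are thus consistent with different alphas.

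**Step 4: share of each cause at n = 59.**

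| Alpha | Assumed rate | r | Power |
|---|---|---|---|
| 0.05 | 93.5% | 54 | 81.6% |
| 0.025 | 93.5% | 55 | 66.2% |
| 0.025 | 93.0% | 55 | 60.3% |

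Alpha accounts for 81.6 − 66.2 = 15.4 points and the rate for 66.2 − 60.3 = 5.9 points. Changing only the rate would not repair the figure: at alpha 0.05 and 93.0% the first n is 67, which has 67.2% power at alpha 0.025.

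**Step 5: sizes for device success at alpha 0.025.**

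| Assumed rate | First n with ≥ 80% | r | Power there | Stays ≥ 80% from | Power at n = 120 (r = 108) |
|---|---|---|---|---|---|
| 93.5% | 81 | 74 | 84.4% | 89 | 95.1% |
| 93.0% | 89 | 81 | 83.0% | 97 | 92.3% |

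The dips are shallow: at 93.5%, 79.6% at n = 87 and 78.7% at 88; at 93.0%, from 79.7% at n = 93 down to 77.1% at 96.

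**Step 6: the floor in Section 9.4.** With 120 enrolled, the number that could be deleted before reaching the floor is:

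- floor 59: 120 − 59 = 61 (51%)
- floor 81: 120 − 81 = 39 (32.5%)
- floor 89: 120 − 89 = 31 (26%)

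**The case against.** The strongest reply is that enrolment makes the error harmless. The plan enrols 120, partly for added certainty, and power at 120 is above 90% at either rate. That stands: a reader might infer that the trial is underpowered, and the documents do not support it. With no dropout rate stated, the analysable number is unknown, but even 102 analysable patients give 87.3% at 93.5% or 82.3% at 93.0%.

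A reader might also blame optimistic expected rates for both sizes. That does not hold. The safety size keeps 81.6% power at the pivotal rate, and most of the effectiveness shortfall is already present at the plan's own 93.5%. Nor is an assumed rate above the pivotal rate an error in itself. Section 9.2 offers the pivotal rates as the basis for the goals, not as predictions for the new graft, and Section 6.3 leaves earlier experience to the Clinical Investigator Brochure, which is not among the documents. What remains is a missing citation.

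A stricter reviewer might call 58 (safety) and 97 (effectiveness) the required sizes, because power stays above 80% from there at the pivotal rates. The plan asks only for 80% power and sets no such criterion, so these are refinements.

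Finally, Section 9.4 states no number and also provides for substituting site measurements and for multiple imputation. Reading 59 as its floor is an inference, though no other effectiveness size is available, and 61 deletions is a ceiling, not a forecast.

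**Conclusion.** The required size for 12-month device success is wrong as written. At the stated exact one-sided 0.025 test, 59 patients give 66.2% power at 93.5% and 60.3% at 93.0%; the first sizes that reach 80% are 81 and 89. The match with alpha 0.05 is the likely explanation, but the documents do not say how 59 was obtained. It does not imply an inflated type I error, because Section 4.3 fixes the test itself at 0.025.

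The safety size and the enrolment of 120 stand. The consequence is confined to the stated size and to the missing-data rule that seems to rely on it. The conclusion assumes independent patients with a common success probability, as the plan's exact binomial test does. The figures for Section 9.4 assume that its threshold is the required size in Section 9.1.

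**What to change.** In Section 9.1, replace 59 with the size recomputed at one-sided alpha 0.025: 81 if 93.5% is kept, or 89 at the pivotal 93.0%. Say which rate is used and why; if no source can be cited for 93.5%, the pivotal rate is the only observed one in the document. Citing a source without recomputing is not enough, since 59 fails at 93.5% too. State that 120 analysable patients give 95.1% or 92.3% power. The safety size of 46 can stay, with a source for 99.2%.

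In Section 9.4, write the floor as a number, using the recomputed effectiveness size in place of 59 for the device-success analysis. If the sponsor wants a floor above which power never falls below 80%, it is 89 at 93.5% or 97 at 93.0%; that is optional.

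The cost is rewording in two sections. Enrolment stays at 120. The stated size becomes less favourable, and the limit on case deletion tightens from 61 patients to 39 or 31.
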